13.1 Sponsor-Investigator Reporting Requirements

13.1.1 Reporting to the Human Research Protection Office (HRPO) at Washington University

Reporting will be conducted in accordance with Washington University IRB Policies.

Pre-approval of all protocol exceptions must be obtained prior to implementing the change.

13.1.2 Reporting to the Quality Assurance and Safety Monitoring Committee (QASMC) at Washington University

The Washington University Sponsor Investigator (or designee) is required to notify the QASMC of any unanticipated problems involving risks to participants or others occurring at WU or any BJH or SLCH institution that has been reported to and acknowledged by HRPO. (Unanticipated problems reported to HRPO and withdrawn during the review process need not be reported to QASMC.)

QASMC must be notified within 10 days of receipt of IRB acknowledgment via email to [contact]. Submission to QASMC must include the myIRB form and any supporting documentation sent with the form.

13.1.3 Reporting to Ichor Medical Systems

Since the TDS-IM device may be involved with the occurrence of adverse events, Ichor Medical Systems will be included in the Adverse Event reporting plan. Reports to Ichor for SAEs or for adverse events with possible relationship to the device should follow the timing for reporting to the WUSM Human Research Protection Office and should be directed to [name] at [contact].

13.1.4 Reporting to AstraZeneca

All SAEs will be reported, whether or not considered causally related to the investigational product, or to the study procedure(s). The reporting period for SAEs is the period immediately following the time that written informed consent is obtained through 90 days after the last dose of durvalumab or until the initiation of alternative anticancer therapy. The investigator and/or Sponsor are responsible for informing the Ethics Committee and/or the Regulatory Authority of the SAE as per local requirements.

The investigator and/or sponsor must inform the FDA, via a MedWatch form, of any serious or unexpected adverse events that occur in accordance with the reporting obligations of 21 CFR 312.32, and will concurrently forward all such reports to AstraZeneca. A copy of the MedWatch report must be emailed to AstraZeneca at the time the event is reported to the FDA. It is the responsibility of the sponsor to compile all necessary information and ensure that the FDA receives a report [according to the FDA reporting requirement timelines](#) and to ensure that these reports are also submitted to AstraZeneca at the same time.

* A **cover page** should accompany the **MedWatch** form indicating the following:

- “Notification from an Investigator Sponsored Study”
- The investigator IND number assigned by the FDA
- The investigator’s name and address
- The trial name/title and AstraZeneca ISS reference number (ESR-16-12613)

* Sponsor must also indicate, either in the SAE report or the cover page, the **causality** of events **in relation to all study medications** and if the SAE is **related to disease progression**, as determined by the principal investigator.

* **Send SAE report and accompanying cover page by way of email to AstraZeneca's designated mailbox: [contact]**

If a non-serious AE becomes serious, this and other relevant follow-up information must also be provided to AstraZeneca and the FDA.

Serious adverse events that do not require expedited reporting to the FDA still need to be reported to AstraZeneca preferably using the MedDRA coding language for serious adverse events. This information should be reported on a monthly basis and under no circumstance less frequently than quarterly.

13.1.4.1 Reporting of deaths to AstraZeneca

All deaths that occur during the study or within the protocol-defined 90-day post-last dose of durvalumab safety follow-up period must be reported to AstraZeneca as follows:

- Death that is clearly the result of disease progression should be documented but not reported as an SAE
- Where death is not due (or not clearly due) to progression of the disease under study, the AE causing the death must be reported to AstraZeneca as an SAE within **24 hours**. The report should contain a comment regarding the co-involvement of progression of disease, if appropriate, and should assign main and contributory causes of death.
- Deaths with an unknown cause should always be reported as an SAE.

Deaths that occur following the protocol-defined 90-day post-last dose of durvalumab safety follow-up period will be documented but will not be reported as an SAE.

13.1.4.2 Definition of adverse events of special interest

An adverse event of special interest (AESI) is one of scientific and medical interest specific to understanding of the Investigational Product and may require close monitoring and rapid communication by the investigator to the sponsor. An AESI may be serious or non-serious. The rapid reporting of AESIs allows ongoing surveillance of these events in order to characterize and understand them in association with the use of this investigational product.

AESIs for durvalumab include but are not limited to events with a potential inflammatory or immune-mediated mechanism and which may require more frequent monitoring and/or interventions such as steroids, immunosuppressants and/or hormone replacement therapy. These AESIs are being closely monitored in clinical studies with durvalumab monotherapy and combination therapy. An immune-mediated adverse event (imAE) is defined as an adverse event that is associated with drug exposure and is consistent with an immune-mediated mechanism of action and where there is no clear alternate etiology. Serologic, immunologic, and histologic (biopsy) data, as appropriate, should be used to support an imAE diagnosis. Appropriate efforts should be made to rule out neoplastic, infectious, metabolic, toxin, or other etiologic causes of the imAE.

If the Investigator has any questions in regards to an adverse event (AE) being an imAE, the Investigator should promptly contact the Clinical Study Lead.

AESIs observed with durvalumab include:

- Diarrhea / Colitis and intestinal perforation
- Pneumonitis / ILD
- ALT/AST increases / hepatitis / hepatotoxicity
- Neuropathy / neuromuscular toxicity (i.e. Guillain-Barré and myasthenia gravis)
- Endocrinopathy (i.e. events of hypophysitis, adrenal insufficiency, diabetes insipidus and hyper- and hypothyroidism and type I diabetes mellitus)
- Rash / Dermatitis

- Nephritis / blood creatinine increases
- Pancreatitis (or labs suggestive of pancreatitis - increased serum lipase, increased serum amylase)
- Myocarditis
- Myositis / Polymyositis
- Other inflammatory response that are rare / less frequent with a potential immune-mediated aetiology include, but are not limited to, pericarditis, sarcoidosis, uveitis and other events involving the eyes, skin, haematological and rheumatological events, vasculitis, non-infectious meningitis and non-infectious encephalitis.

In addition, infusion-related reactions and hypersensitivity/anaphylactic reactions with a different underlying pharmacological aetiology are also considered AESIs.

Further information on these risks (e.g. presenting symptoms) can be found in the current version of the durvalumab Investigator Brochure. More specific guidelines for their evaluation and treatment are described in detail in the Dosing Modification and Toxicity Management Guidelines. These guidelines have been prepared to assist the Investigator in the exercise of his/her clinical judgment in treating these types of toxicities. These guidelines apply to AEs considered causally related to the study drug/study regimen by the reporting investigator.

13.1.4.3 Hy's Law

Cases where a patient shows elevations in liver biochemistry may require further evaluation and occurrences of AST or ALT \geq 3x ULN together with total bilirubin \geq 2x ULN may need to be reported as SAEs. Please refer to the Dosing Modification and Toxicity Management Guidelines for further instructions on cases of increases in liver biochemistry and evaluation of Hy's law.

13.1.4.4 Overdose

An overdose is defined as a subject receiving a dose of durvalumab in excess of that specified in the Investigator's Brochure, unless otherwise specified in this protocol.

Any overdose of a study subject with durvalumab, with or without associated AEs/SAEs, is required to be reported within 24 hours of knowledge of the event to the sponsor and AstraZeneca/MedImmune Patient Safety or designee using the designated Safety e-mailbox. If the overdose results in an AE, the AE must also be recorded as an AE. Overdose does not automatically make an AE serious, but if the consequences of the overdose are serious, for example death or hospitalization, the event is serious and must be recorded and reported as an SAE. There is currently no specific treatment in the event of an overdose of durvalumab.

The investigator will use clinical judgment to treat any overdose.

13.1.4.5 Hepatic function abnormality

Hepatic function abnormality that fulfills the biochemical criteria of a potential Hy's Law case in a study subject, with or without associated clinical manifestations, is required to be reported as "hepatic function abnormal" **within 24 hours of knowledge of the event** to the sponsor and AstraZeneca Patient Safety using the designated Safety e-mailbox, unless a definitive underlying diagnosis for the abnormality (e.g., cholelithiasis or bile duct obstruction) that is unrelated to investigational product has been confirmed.

- If the definitive underlying diagnosis for the abnormality has been established and is unrelated to investigational product, the decision to continue dosing of the study subject will be based on the clinical judgment of the investigator.
- If no definitive underlying diagnosis for the abnormality is established, dosing of the study subject must be interrupted immediately. Follow-up investigations and inquiries must be initiated by the investigational site without delay.

Each reported event of hepatic function abnormality will be followed by the investigator and evaluated by the sponsor and AstraZeneca/MedImmune.

13.1.4.6 Pregnancy

If a patient becomes pregnant during the course of the study, the IPs should be discontinued immediately.

Pregnancy itself is not regarded as an AE unless there is a suspicion that the IP under study may have interfered with the effectiveness of a contraceptive medication. Congenital abnormalities or birth defects and spontaneous miscarriages should be reported and handled as SAEs. Elective abortions without complications should not be handled as AEs. The outcome of all pregnancies (spontaneous miscarriage, elective termination, ectopic pregnancy, normal birth, or congenital abnormality) should be followed up and documented even if the patient was discontinued from the study.

If any pregnancy occurs in the course of the study, then the Investigator or other site personnel should inform the appropriate AstraZeneca representatives within 1 day, ie, immediately, but **no later than 24 hours** of when he or she becomes aware of it.

The designated AstraZeneca representative will work with the Investigator to ensure that all relevant information is provided to the AstraZeneca Patient Safety data entry site within 1 to 5 calendar days for SAEs and within 30 days for all other pregnancies.

The same timelines apply when outcome information is available.

13.1.5 Reporting to the FDA

The conduct of the study will comply with all FDA safety reporting requirements. **PLEASE NOTE THAT REPORTING REQUIREMENTS FOR THE FDA DIFFER FROM REPORTING REQUIREMENTS FOR HRPO/QASMC.** It is the responsibility of the Washington University Sponsor-Investigator to report to the FDA as follows:

- Report any unexpected fatal or life-threatening suspected adverse reaction (refer to Appendix B for definitions) no later than 7 calendar days after initial receipt of the information.
- Report a suspected adverse reaction that is both serious and unexpected (SUSAR, refer to Appendix B) no later than 15 calendar days after it is determined that the information qualifies for reporting. Report an adverse event (refer to Appendix A) as a suspected adverse reaction only if there is evidence to suggest a causal relationship between the drug and the adverse event, such as:
 - A single occurrence of an event that is uncommon and known to be strongly associated with drug exposure
 - One or more occurrences of an event that is not commonly associated with drug exposure but is otherwise uncommon in the population exposed to the drug
 - An aggregate analysis of specific events observed in a clinical trial that indicates those events occur more frequently in the drug treatment group than in a concurrent or historical control group
- Report any findings from epidemiological studies, pooled analysis of multiple studies, or clinical studies that suggest a significant risk in humans exposed to the drug no later than 15 calendar days after it is determined that the information qualifies for reporting.
- Report any findings from animal or in vitro testing that suggest significant risk in humans exposed to the drug no later than 15 calendar days after it is determined that the information qualifies for reporting.
- Report any clinically important increase in the rate of a serious suspected adverse reaction of that listed in the protocol or IB within 15 calendar days after it is determined that the information qualifies for reporting.

Submit each report as an IND safety report in a narrative format or on FDA Form 3500A or in an electronic format that FDA can process, review, and archive. Study teams must notify the Siteman Cancer Center Protocol Development team of each potentially reportable event within 1 business day after initial receipt of the information, and must bring the signed 1571 and FDA Form 3500A to the Siteman Cancer Center Protocol Development team no later than 1 business day prior to the due date for reporting to the FDA.

Each notification to FDA must bear prominent identification of its contents (“IND Safety Report”) and must be transmitted to the review division in the Center for Drug Evaluation and Research (CDER) or in the Center for Biologics Evaluation and Research (CBER) that has responsibility for review of the IND. Relevant follow-up information to an IND safety report must be submitted as soon as the information is available and must be identified as such (“Follow-up IND Safety Report”).

13.1.6 Reporting to the Institutional Biosafety Committee

In accordance with institutional policies and NIH guidelines, any unanticipated problems must be reported to the Institutional Biological and Chemical Safety Committee (IBC) at Washington University School of Medicine.

The Washington University Sponsor-Investigator (or designee) must report the following events to the Biosafety Officer at the time of submission to HRPO:

- Any overt personnel exposure to recombinant DNA-containing material, whether or not that exposure leads to illness
- Any significant spill of recombinant DNA-containing material outside of a biological safety cabinet, where a significant spill is:
 - A spill of recombinant risk group 1 agent-containing material which requires remediation by EH&S or other first responders
 - A spill of recombinant risk group 2 agent-containing material which is greater than 1 liter
 - Any size spill of risk group 3 agent-containing material or material the IBC has mandated to be handled using BSL2+ practices and procedures
- Any incident which results in the release of recombinant DNA to the environment

In addition, the IBC must be informed of the following events:

- Any serious adverse event which is both unexpected and associated with the use of the gene transfer product

The Biosafety Officer may be contacted at [contact].

When submitting reports to the IBC, the FDA MedWatch form will be used. The Washington University Sponsor-Investigator (or designee) will be responsible for submitting all MedWatch forms from secondary sites to the IBC.

WUSM IBC guidelines specify that any study modifications related to the investigational agent as well as the IRB renewal paperwork should be sent to the IBC for approval (if a modification) or acknowledgment (if an annual renewal). The IRB and IBC will review all submissions simultaneously.

14 DATA AND SAFETY MONITORING

14.1 Protocol stopping criteria

The principal investigator will closely monitor and analyze study data as they become available and will make determinations regarding the presence and severity of adverse events. The administration of study injections and new enrollments will be halted and the QASMC promptly notified if any of the following events occurs:

- (1) **One** (or more) subject(s) experiences a Grade 3 or 4 adverse event that is classified as probably or definitely related to treatment with durvalumab or vaccination;
- (2) **One** (or more) subject(s) experiences an SAE related to either durvalumab or vaccine;
- (3) **Two** (or more) subjects experience the **same** Grade 2 or higher adverse event that is classified as probably or definitely related to durvalumab or vaccination: this criterion applies to fever, vomiting, laboratory abnormalities or other clinical adverse experiences, but does not apply to the subjective local or systemic symptoms of pain/tenderness, malaise, fatigue, headache, chills, nausea, myalgia, or arthralgia.
- (4) Death (other than death related to progressive disease) that occurs within 30 days after receiving DNA vaccination.
- (5) Any other observation occurs that in the opinion of the PI results in a recommendation to halt enrollment.

If one of these events does occur, study injections and study enrollments would only resume if review of the adverse events that caused the halt resulted in a recommendation to permit further study injections and study enrollments.

The QASMC, in consultation with the principal investigator, will conduct any review and make the decision to resume or close the study for any Grade 2 or 3 events leading to a halt in the study.

The QASMC, with participation by the principal investigator, will consult with the FDA to conduct the review and make the decision to resume or close the study for all Grade 4 adverse events leading to a halt in the study.

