8 TREATMENT PLAN

8.1 Neoantigen DNA vaccine administration

The first neoantigen DNA vaccine injection will take place following completion of SOC therapy. The day of the first vaccine injection will be referred to as Day 1.

All subjects will be treated as outpatients in the Siteman Cancer Center.

The schedule of vaccination is Day 1, Day 29 \pm 7, Day 57 \pm 7, Day 85 \pm 7, Day 113 \pm 7, and Day 141 \pm 7 with at least 21 days between injection days. All study injections will be given intramuscularly using an integrated electroporation device (TDS-IM system, Ichor Medical Systems). At each vaccination time point, patients will receive two injections of the neoantigen DNA vaccine, one injection into each deltoid or lateralis. If both injections cannot be given on the same day, the patient will be asked to return to complete the second injection. Standard aseptic technique and precautions will be utilized in site preparation, vaccine administration, and medical waste disposal to ensure maximal safety of subjects and study personnel. Participants' vital signs will be monitored for 30 minutes post vaccine for safety purposes.

The propagation of electroporation inducing electrical fields in the muscle will result in brief, localized muscle contractions at the site of administration, which are transiently painful. The neoantigen DNA vaccines will be administered by an experienced nurse who has completed a training seminar on the use of the TDS-IM device.

The sites of immunization may be rotated for each of the immunizations. No injection will be given at a location in which the draining lymph nodes have been removed.

At the discretion of the treating physician, patients may be pre-medicated with lorazepam 1mg PO (or similar) at least 30 minutes but no greater than 60 minutes prior to the first injection. Patients may also receive a second dose of lorazepam (1 mg PO) (or similar) 10 minutes prior to injection. Patients may also receive pain medication at treating physicians' discretion PO at least 30 minutes but no greater than 60 minutes prior to the first injection.

At intervals throughout the study (both before and after vaccination) subjects will have blood drawn for immunologic assays. Any cells, serum or plasma not used will be stored for future immunological assays.

Please see **Section 10 Study Calendar** for details on study visit procedures and monitoring.

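### Section 14.1: durvalumab-related events trigger the halt, but durvalumab infusions are not named among the treatments to be stopped or restarted

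*Combined protocol and SAP*

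**What the plan says.** **Triggers.** Section 14.1 lists five events that stop the study. Three of them name durvalumab. Trigger (1) is a Grade 3 or 4 adverse event "classified as probably or definitely related to treatment with durvalumab or vaccination". Trigger (2) is a subject who "experiences an SAE related to either durvalumab or vaccine". Trigger (3) is the same Grade 2 or higher event in two or more subjects, again related to either agent.

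**Action.** "The administration of study injections and new enrollments will be halted", and the safety monitoring committee (QASMC) is notified.

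**Restart.** After a halt, "study injections and study enrollments would only resume if review of the adverse events that caused the halt" ends in a favourable recommendation, which is again worded in terms of injections and enrolment only.

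**Review.** The committee, with the principal investigator, is to "make the decision to resume or close the study for any Grade 2 or 3 events leading to a halt in the study". A parallel sentence brings in the FDA for Grade 4 events.

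**Meaning of the term.** Section 8.1, on vaccine administration, says: "All study injections will be given intramuscularly using an integrated electroporation device". Section 5.6 gives durvalumab as an intravenous infusion over about 60 minutes, and 8.2 speaks of vaccine injections and durvalumab infusions as two different things.

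**The concern.** The triggers cover two agents, and the consequence names one. Staff who apply the halt and restart sentences as worded, with the meaning that 8.1 gives to the term, would cancel vaccinations and stop enrolling. They would find no instruction to withhold durvalumab from patients other than the one who had the event. If the trigger was durvalumab-related, the agent under suspicion is the one that the rule leaves out.

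Safety is the primary objective. A study-wide stopping rule exists to protect patients who have not yet had the event while the committee decides whether to go on. Its scope should be plain to the person holding the infusion bag.

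**Working it through.** The plan states no figure on this point, so the check is mainly a comparison of texts.

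**1. Terms in 14.1.**

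| Part of 14.1 | *study injections* | *durvalumab* |
|---|---|---|
| Triggers (1), (2), (3) | 0 | 3 (one each) |
| Halt sentence | 1 | 0 |
| Restart sentence | 2 | 0 |
| Total | 3 | 3 |

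The two terms never meet: durvalumab appears only as a cause of the halt, and study injections only as what is halted or resumed.

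**2. Does another section suspend durvalumab in other patients?**

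- Section 9.3 holds or discontinues durvalumab according to the toxicity of the affected patient. It contains no hold across patients and does not refer to Section 14.
- Section 9.4, on the vaccine, does refer the reader to the Section 14 stopping criteria.
- Section 12.1 says that subjects *may* be removed from protocol therapy. Most items concern that subject's own course. Items (11), the subject's best interest, and (12), administrative reasons including study termination, are not limited to the patient who had the event. Both are discretionary and neither is an automatic hold.

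**3. Which infusions would a vaccine halt interrupt in practice?** From the Section 10 calendar and the Section 16 form schedule:

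- Durvalumab visits: Days 85, 113, 141, 169 = 4.
- Of these, also vaccine visits: Days 85, 113, 141 = 3.
- Durvalumab without vaccine: 4 − 3 = 1, Day 169, which the calendar marks as for the durvalumab group only.

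At three of the four visits a cancelled vaccination would draw attention to the halt. At Day 169 there is no vaccination to cancel.

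**4. Could durvalumab alone fire the rule?** Section 2.10.5 reports that about 3.5% of subjects in monotherapy studies had a serious adverse event judged related to durvalumab. Assume that this rate applies here, although this trial gives at most four doses and combines them with a vaccine. The chance of at least one such event among n patients is 1 − (1 − 0.035)^n:

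- n = 12 (24 patients randomized 1:1, Section 4.6): 1 − 0.965^12 = 34.8%.
- n = 10 (evaluable per arm, Section 15.2.1): 1 − 0.965^10 = 30.0%.

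One such event is enough for trigger (2). These figures show only that a durvalumab-driven halt is plausible. They are not the chance that anyone is infused during a halt, which cannot be computed because the documents give no accrual rate and so no count of patients due a dose at a given time.

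**The case against.** The strongest reply is that 14.1 must be read whole. Its last two sentences speak of a halt in the study and of a decision to resume or close the study. A study that has to be resumed is not naturally one in which one of its two agents is still being given.

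Section 8.7 supports this reading. Directly after stating the maximum number of durvalumab doses, it speaks of terminating subjects from further injections and sends the reader to Section 12, where one removal criterion is a Grade 3 or higher infusion reaction. There, injections looks like shorthand for protocol therapy as a whole. The sentence in 8.1 describes a route of administration and is not a formal definition.

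The setting also lowers the risk. This is one institution with 24 patients; every effort is to be made to give both agents on the same day (8.2); and toxicities are reviewed at a weekly meeting (14.3). Because 14.1 names durvalumab in three triggers, it applies without a pointer from 9.3, so the missing cross-reference is weak evidence by itself.

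Most of this stands. It makes a full halt the likelier intention and a mistaken infusion less likely. But the review sentences say who decides and what is decided, not which treatments stop meanwhile. Same-day dosing is an aim, and it cannot apply at Day 169. Loose use of the term in 8.7 makes the halt sentence ambiguous, which is a reason to correct it.

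**Conclusion.** The point holds as a gap in the scope of a safety rule. Durvalumab is in the triggers and is not named in the halt or restart sentence; the natural meaning of the term used there is the vaccine; and no other section supplies an automatic hold for other patients. The exposure is clearest at one of four scheduled infusions, Day 169.

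A reader might infer that the sponsor chose to keep giving durvalumab during a halt, or that 14.1 as a whole plainly lets infusions continue. The documents support neither. Nothing states such a choice, and the references to halting, resuming or closing the study lean the other way. What can be said is that durvalumab is not named, and that someone following the operative sentences exactly would not be told to stop it.

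The textual gap is certain and the intention probably benign. The sentences should be corrected because they govern patient safety and the change is small. The conclusion rests on reading *study injections* as in 8.1 and 8.2. No number of patients harmed or exposed is claimed.

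**What to change.** Make three replacements in two sentences of 14.1 and add one cross-reference:

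- Halt sentence: *The administration of vaccine injections and durvalumab infusions, and new enrollments, will be halted*, with the rest unchanged.
- Restart sentence: replace both mentions of *study injections* with *vaccine injections and durvalumab infusions*.
- Section 9.3: add the pointer to the Section 14 stopping criteria that 9.4 already has.

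This needs a protocol amendment, with no new data or visits. If a full halt was always meant, it changes no policy.

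The downside is that durvalumab doses in other patients may be delayed during a halt. Section 15.2.1 bases the between-arm immune comparison on Days 113 and 169, so a delay may shift durvalumab exposure at those samples. Recording actual infusion dates against sample dates would let the analysis describe any such shift.

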13 REGULATORY AND REPORTING REQUIREMENTS

The entities providing oversight of safety and compliance with the protocol require reporting as outlined below. Please refer to 20.4 for definitions and 20.5 for a grid of reporting timelines.

Adverse events will be tracked from start of treatment through 90 days after the last dose of Durvalumab or until initiation of new anticancer therapy, whichever comes first. All adverse events must be recorded on the toxicity tracking case report form (CRF) with the exception of:

- Baseline adverse events, which shall be recorded on the medical history CRF

Refer to the data submission schedule in Section 16 for instructions on the collections of AEs in the EDC.

Reporting requirements for Washington University study team are found in section 13.1.

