16.1 Adverse Event Collection in the Case Report Forms

All adverse events that occur beginning with start of treatment (minus exceptions defined in Section 13) must be captured in the Toxicity Form. Baseline AEs should be captured on the Medical History Form.

Participant death due to disease progression should be reported on the Toxicity Form as grade 5 disease progression. If death is due to an AE (e.g. cardiac disorders: cardiac arrest), report as a grade 5 event under that AE. Participant death must also be recorded on the Death Form.

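### Stopping criterion 4 in section 14.1 runs its death clock from DNA vaccination only, so on the nominal schedule it closes two days after the last durvalumab dose

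*Combined protocol and SAP*

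**What the plan says.** Section 14.1 lists five events that halt the study.

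- Criteria 1 and 3 need an event classed as probably or definitely related to durvalumab or vaccination. Criterion 1 is limited to Grade 3 or 4, and criterion 3 needs the same event in two subjects.
- Criterion 2 applies when a subject "experiences an SAE related to either durvalumab or vaccine".
- Criterion 4 is "Death (other than death related to progressive disease) that occurs within 30 days after receiving DNA vaccination".
- Criterion 5 is "Any other observation occurs that in the opinion of the PI results in a recommendation to halt enrollment".

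When a criterion is met, "The administration of study injections and new enrollments will be halted and the QASMC promptly notified". Afterwards, "study injections and study enrollments would only resume if review of the adverse events that caused the halt resulted in a recommendation". The QASMC, in consultation with the principal investigator, decides on Grade 2 or 3 events. The QASMC, consulting the FDA, is to "make the decision to resume or close the study for all Grade 4 adverse events leading to a halt in the study". A death due to an adverse event is coded differently: section 16.1 says to "report as a grade 5 event under that AE".

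The last vaccination is on Day 141 (section 8.1). Up to four durvalumab doses are allowed (section 8.7), on Days 85, 113, 141 and 169 (sections 10 and 16). Adverse events are tracked "through 90 days after the last dose of Durvalumab or until initiation of new anticancer therapy, whichever comes first" (section 13), and section 13.1.4.1 uses the same 90 days for reporting deaths.

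**The concern.** Criteria 1 to 3 all name durvalumab beside the vaccine. Criterion 4 does not, yet it is the one death trigger that works when the cause is unclear or the investigator does not attribute the death to treatment. In a small trial of a new combination, a trigger of that kind guards against an attribution that later proves wrong.

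Take a non-progression death on Day 180, 11 days after the last durvalumab dose and 39 days after the last vaccination. If it is not classed as related, section 14.1 requires no halt. The same death with the same classification, 11 days after a vaccination, must halt the study. Safety of the combination is part of the primary objective (section 15.1.1), so the rule should follow both agents.

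**Working it through.** The plan gives no derived figure to reproduce. The check is a day count from stated inputs.

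**Inputs.** Criterion 4 window: 30 days from vaccination (14.1). Last vaccination: Day 141 ±7 (8.1). Last durvalumab dose: Day 169 (10 and 16), with ±7 days on the four-week interval (8.2). Durvalumab safety period: 90 days after the last dose (13 and 13.1.4.1).

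**Nominal full course.**
- Criterion 4 closes: 141 + 30 = Day 171.
- Safety period: Day 169 + 1 = 170 to Day 169 + 90 = 259.
- Covered: Days 170 and 171, so 2 days.
- Not covered: 259 − 171 = 88 days (Days 172 to 259), and 88/90 = 97.8%.

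**Visit windows.** Uncovered days = 90 − max(0, 30 − gap), where gap is the last durvalumab day minus the last vaccine day.
- Last vaccine Day 134 to 148 and last durvalumab Day 162 to 176 give a gap of 14 to 42 days.
- Gap 14: 90 − 16 = 74 uncovered. Gap of 30 or more: 90 uncovered.
- If the gap is held to 28 ± 7 days (21 to 35), the range is 81 to 90.

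**Durvalumab stopped early, vaccination continued to Day 141.** The criterion still closes on Day 171.
- Last dose Day 141: 141 + 90 = 231, and 231 − 171 = 60 uncovered.
- Last dose Day 113: 203 − 171 = 32 uncovered.
- Last dose Day 85: 175 − 171 = 4 uncovered.

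**Effect of a durvalumab anchor, nominal full course.**
- 30 days: 169 + 30 = Day 199. This closes Days 172 to 199 (28 days) and leaves 88 − 28 = 60.
- 90 days: closes all 88.

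**Exposure.** Section 2.10.2 gives an expected half-life of about 21 days. Assuming simple exponential decline, the fraction of the last dose remaining is 0.5^(3/21) = 0.91 on Day 172, 0.5^(30/21) = 0.37 at 30 days and 0.5^(90/21) = 0.05 at 90 days. The trigger therefore closes while most of the last dose is still present.

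**Which criteria reach the death.** For a non-progression death on Days 172 to 259 not classed as related, criteria 1, 2 and 3 fail on relatedness and criterion 4 fails on time. Criterion 5, the principal investigator's opinion, is the only one left.

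**The case against.** The case on the other side has real substance.

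- **The 90 days is a tracking and reporting period.** Nothing in the protocol makes it a stopping window, and the vaccine's own 30-day trigger is also much shorter than its follow-up. This stands. It means that 88 days measures the gap against the safety period and is not a breach of a stated rule. With a matching 30-day anchor, the gap to close is 28 days.
- **The count assumes all four doses.** This also stands: with early durvalumab stopping and continued vaccination, 60, 32 or 4 days are uncovered.
- **The vaccine is the newer agent.** Section 2.10 reports more than 1800 subjects given durvalumab, so a broader trigger for the vaccine could be deliberate. The protocol does not give this reason, and the combination itself is under test.
- **Other controls exist.** A reader might infer that a late death on durvalumab could be stopped on only by the principal investigator, or that nobody else would look at it. The documents do not support that. Criterion 2 halts for any related serious event with no time limit. Non-progression deaths go to AstraZeneca within 24 hours (13.1.4.1). Toxicities are reviewed weekly and study data monthly (14.3). The cancer center, the HRPO and the FDA are among those who can end the study (12.1 and 18.3). None of these, however, is a halt that a death sets off by rule.
- **Criterion 4 also needs a judgement**, namely that the death is not due to progression. True, but that is a different question from whether treatment caused it.

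A reader might also infer that infusions may continue during a halt, because the halt and resume sentences mention injections, which section 8.1 describes as intramuscular. Section 14.1 also speaks of a halt in the study as a whole, so that reading is strained. Likewise, the absence of a Grade 5 route does not leave a death unreviewed: the QASMC is notified of every halt, and restart needs a favourable review. Both are matters of wording.

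**Conclusion.** The point holds as a mismatch between a vaccine-only death trigger and a two-agent regimen. On the nominal full course, criterion 4 lapses two days after the last durvalumab dose. For the remaining 88 of 90 days of the safety period, a non-progression death not classed as related triggers no mandatory halt. The figure rests on six vaccinations, four durvalumab doses and no new anticancer therapy before Day 259.

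These are calendar days and do not measure risk. The documents give no death rate, so the chance of such a death cannot be estimated, and the gap does not show that the trial is unsafe. The change is worth making because the hole is specific and cheap to close.

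**What to change.** In section 14.1, add a durvalumab anchor to criterion 4.

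- **Minimum:** apply the same 30 days after a durvalumab dose as after vaccination. On the nominal schedule this closes Days 172 to 199.
- **Preferred:** keep 30 days after vaccination and add 90 days after a durvalumab dose, or until new anticancer therapy starts if sooner. This uses the protocol's own safety period and closes all 88 days.

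Two minor wording changes belong in the same section. Name durvalumab infusions beside injections in the halt and resume sentences; this matters most for the Day 169 infusion, the only one scheduled without a vaccination. Extend the FDA-consulted review from Grade 4 to Grade 5 events and any death under criterion 4.

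No new visits or data are needed, since adverse events and deaths are already followed over this period. The cost is an occasional halt, review and FDA consultation for a death that proves clearly unrelated, such as an accident on Day 250. The 30-day version would incur this less often, but leaves 60 days open.
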